## **6 Ethical and Legal Issues**

### **6.1 Confidentiality**

All patient information will remain confidential and stored on Partners computers. Identifiers such as name will only be used during the initial data retrieval process and can be destroyed once all data records have been obtained and data analysis completed.

## **7 Statistical Analysis**

### **7.1 Study Endpoints:**

#### **7.1.1 Primary Endpoint:**

The primary endpoint of Phase 1 is developing a finalized version of the psychological intervention for caregivers of patients undergoing HCT based on the findings from the qualitative data analysis.

#### **7.2 Sample Size Calculation:**

We will recruit and consent 5-10 caregivers for Phase 1. Based on our team's prior qualitative research experience, we believe that this sample size will be sufficient to achieve thematic saturation.

#### **7.3 Analysis Plan:**

**Phase 1 Data Analysis and Interpretation:** We will use descriptive statistics to summarize the demographic and clinical characteristics of the caregivers enrolled in the study. Our planned sample size (n = 5-10) will allow us to collect comprehensive feedback about the intervention and ensure that we have sufficient number of participants to achieve thematic saturation. The qualitative component of the

Psychological Intervention to Promote Coping for Caregivers of Patients Undergoing Hematopoietic Stem Cell Transplantation (HCT)  
Protocol version 1/ 10-3-2016

exit interviews will 1) explore caregiver perception of the acceptability and content of the intervention; and 2) explore caregiver perceptions of the benefits of receiving the intervention. We will also evaluate the acceptability of the intervention by exit interview responses. We will analyze the qualitative data from the exit interview according to the NIH-Best Practices for Mixed Methods research in Health Sciences for applicability, preferences, clinical relevance, intervention length/timing, and challenges. Study staff will independently review the qualitative interview transcripts to create a thematic framework for interpretation. Two independent coders (Drs. [name] and [name]) will independently code the data to enhance validity and credibility, until high reliability is achieved (Kappa >0.080). Discrepancies will be resolved by comparison to raw data and reviews by Drs. [name], [name], [name], and [name].

We will utilize the qualitative data obtained from phase 1 and clinicians' experience to finalize the multicomponent psychological intervention. Specifically, we will refine the following aspects of the intervention:

- **Intervention content:** We will use caregivers' feedback to confirm the relevance of the intervention content, and to revise content as needed. For instance, if caregiver report that they would have liked to focus on more active coping strategies, we will increase the balance between change- and acceptance-oriented (e.g., mindfulness) approaches. To further enhance the intervention, we also may integrate caregivers' real-life concerns as examples throughout the protocol when introducing the use of coping skills and strategies.
- **Program structure and schedule:** We anticipate that caregivers will have different needs during their loved ones' hospitalization for HCT vs. the immediate post-transplant period. However, we will use caregivers' feedback to guide the order and timing of the eight intervention sessions during these two periods. Additionally, we may revise session number (8 sessions) or length (30-45 min per session) based on caregivers' feedback about participation burden and utility.
- **Program modality:** We will use exit interview data to determine whether the delivery of the intervention visit in-person or over the phone was acceptable to participants.
- **Additional areas of concern:** We will identify any additional areas of concern from caregivers that were not addressed specifically in the intervention and integrate them in a revised intervention manual.

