**Addressing the needs of caregivers is necessary to improve both patients' and caregivers' outcomes**

Caregiving burden often leads to substantial negative effects on caregivers' quality of life (QOL) and mood. In fact, more than a quarter of caregivers of HCT recipients experience significant depression and anxiety symptoms. Fatigue, sleep disturbances, and difficulty maintaining work are common challenges seen in this population. We have conducted a prospective longitudinal study of patients and caregivers during hospitalization for HCT (see preliminary studies), which demonstrates that caregivers experience a substantial decline in QOL and increase in depression symptoms during the HCT process. Hence, addressing the needs of caregivers has the potential to substantially impact their experience and overall QOL. Moreover, as caregivers provide the majority of care for patients undergoing HCT, attending to their needs is an essential step in ensuring the delivery of high-quality care for patients with hematologic malignancies.

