### **4 Research Subject Selection**

#### **4.1 Study Subject Selection:**

During phase 1, we will use qualitative data to refine the multicomponent psychological intervention specifically targeting the needs of caregivers during their loved ones' hospitalization for HCT and in the first 100 days post-HCT. We will recruit 5-10 adult caregivers of patients undergoing HCT at MGH to participate in phase 1 of this project. Caregivers will be recruited during the patient transplant consent visit, which typically occurs 2-4 weeks prior to admission for HCT. Caregivers are required to attend the HCT consent visit with the patient.

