#### *Caregivers Exclusion Criteria:*

- 1) Significant uncontrolled psychiatric disorder (psychotic disorder, bipolar disorder, major depression) or other co-morbid disease (dementia, cognitive impairment), which the treating clinician believes prohibits the ability to participate in study procedures.

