## **5 Research Subject Entry**

### **5.1 Study Research Subject Entry**

A total of 5-10 caregivers of patients undergoing HCT will participate in phase 1 of this study. The research team will review the transplant clinic schedule to identify potentially eligible caregivers for study participation. We will approach caregivers to participate in phase 1 during the outpatient clinic visit when their loved ones' consent for HCT, which typically occurs 2-4 weeks prior to HCT. Patients are required to be accompanied by a caregiver for the consent visit. The research team will contact eligible participants' oncology clinicians to inform them that we plan to approach the caregiver and inquire about any concerns regarding their participation. If the clinician objects to the caregivers' participation, we will document the reason and not approach those individuals.

If the oncologist has no concerns regarding the caregivers' participation, the research staff will approach eligible caregivers immediately after the transplant consent clinic visit. The research assistant (RA) will review the consent form with potential participants, which will clearly detail the nature of the study procedures and the time requirement. The RA will obtain written informed consent from participants and provide them with a copy of the signed consent form.

Enrolled caregivers will complete a baseline self-report questionnaire (Appendix A) at the time of obtaining informed consent for the study or within the 72-hour window from study enrollment. Caregivers who provide informed consent and complete the baseline questionnaire will then be registered with ODQ and scheduled for their first study intervention visit either in-person or via telephone. The RA will be responsible for contacting ODQ. The ODQ will require a copy of the caregivers' informed consent and eligibility checklist.

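### Is a sample of 5-10 caregivers too small for the assurance in 7.3 that thematic saturation will be reached?

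*Combined protocol and SAP*

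**What the plan says.** Phase 1 is a qualitative refinement step. Its primary endpoint (7.1.1) is a finalized version of the intervention, and no hypothesis is tested. On sample size, 7.2 states "We will recruit and consent 5-10 caregivers for Phase 1" and, citing the team's experience, "we believe that this sample size will be sufficient to achieve thematic saturation". Section 7.3 repeats the range and says that it will "ensure that we have sufficient number of participants to achieve thematic saturation". The same range appears under Study Subject Selection (4.1) and Study Research Subject Entry, so the count itself is consistent.

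No calculation supports the range. The plan gives no definition of saturation, no rule for continuing or stopping interviews, and no allowance for consented caregivers who give no exit interview.

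Two other statements bear on the point. The background (2.2) reports that "more than a quarter of caregivers of HCT recipients experience significant depression and anxiety symptoms". Recruitment is from clinic lists: "The research team will review the transplant clinic schedule to identify potentially eligible caregivers for study participation". Caregivers are not selected by symptom level.

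**The concern.** Section 7.3 turns a belief into an assurance and applies it to the whole range, including five. A theme can be found only if at least one interviewee holds it. With five interviews, a view confined to a quarter of caregivers could easily have no holder in the room.

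The stakes would be in the manual. Section 7.3 promises "We will identify any additional areas of concern from caregivers that were not addressed specifically in the intervention and integrate them" in a revised manual, which then goes into a pilot randomized trial of 100 caregivers with mood among its outcomes. At the same 25% rate, about 25 of those 100 would belong to the symptomatic group. A need peculiar to that group could pass through Phase 1 unseen.

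**Working it through.** **The plan's own figure.** The range 5-10 rests on experience, with no formula or numerical input, so there is nothing to reproduce.

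**Inputs for the check.** The number interviewed is n = 5 or 10 (7.2, 7.3). The share with significant depression and anxiety symptoms is p = 0.25, the boundary of the more-than-a-quarter statement in 2.2. The share among those actually enrolled is not given. It could be higher than 0.25. It could also be lower, because uncontrolled major depression can exclude a caregiver and an objection from the oncology clinician stops the approach. The other values of p below are therefore assumptions. Sampling is taken as independent and representative.

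**Formula.** P(no such caregiver among n) = (1 - p)^n.

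| Share p | n = 5 | n = 10 |
|---|---|---|
| 0.15 | 0.85^5 = 44.4% | 0.85^10 = 19.7% |
| 0.20 | 0.80^5 = 32.8% | 0.80^10 = 10.7% |
| 0.25 | 0.75^5 = 23.7% | 0.75^10 = 5.6% |
| 0.30 | 0.70^5 = 16.8% | 0.70^10 = 2.8% |
| 0.35 | 0.65^5 = 11.6% | 0.65^10 = 1.4% |

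Since 2.2 says more than a quarter, the 24% and 6% are upper limits for a representative sample. They would be exceeded only if screening lowers the share or interviews are lost.

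**Lost interviews.** The plan counts consents, but the data come from exit interviews around day +90. Suppose each consented caregiver has a 20% chance of giving no interview (an assumption, borrowed from the missing-data rate of the team's earlier longitudinal study). Then P(none) at p = 0.25 is (1 - 0.25 × 0.8)^n = 0.80^n, which is 32.8% for 5 consented and 10.7% for 10.

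**What the figures measure.** They give the chance that one clinical subgroup is absent. Saturation in 7.3 concerns what caregivers say about the intervention: whether it applies to them and is clinically relevant, what they prefer, session length and timing, and difficulties met. For the percentages to bear on saturation, caregivers with depression or anxiety symptoms would need views on these topics that no other caregiver shares. The protocol does not say so.

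**Other routes into the manual.** The draft content was built from a literature review and a longitudinal study of 90 patients and 70% of their caregivers (0.70 × 90 = 63 if each patient had one). Two of the eight sessions already deal with coping and emotions. Clinicians' experience also feeds the final version. Timing, convenience, phone delivery, number of sessions and session length have fixed items in the interview guide, so any caregiver can inform them.

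**The case for a change.** The best case for a change is that the calculation tests a necessary condition: a theme that no interviewee holds cannot be found. None of the chances for n = 5 in the table, from 12% to 44%, fits a guarantee. The baseline questionnaire is demographic only, so the study could not show afterwards whether symptomatic caregivers were interviewed. Aiming for ten stays within the range. Compared with stopping at five, it would cost 5 × 8 sessions × 30-45 minutes = 20-30 therapist hours, plus 5 × 30 minutes = 2.5 interview hours.

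Much of this stands. The verb in 7.3 is stronger than the support in 7.2, the low end of the range covers minority views poorly, and how saturation will be judged is unstated. Two steps fail, however. The plan does not commit to stopping at five; ten is already allowed, so making it the target is a preference for enrolling more and corrects no figure the plan misses. Nor would writing a coverage figure into 7.3 help. The 94% for ten interviews (1 - 0.056) needs every one of at most ten consented caregivers to be interviewed. With eight completed it is 1 - 0.75^8 = 90%, and under the 20% random loss above it is 1 - 0.107 = 89%. It also presumes chance sampling from a single clinic that applies a psychiatric exclusion and clinician objections. One loose assurance would give way to another that looks more precise.

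**Conclusion.** No change is called for. The discrepancy is one of wording: 7.3 asserts what 7.2 only expects. A reader can take the expectation in 7.2 as the basis, and coders working through the transcripts will see whether new codes are still appearing and can report it. That gap is one analysts fill as a matter of course.

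The size of the illustration is 24% with five interviews and 6% with ten, at a 25% share, with chance sampling and no lost interviews. Both fall if the share is higher and rise if screening or lost interviews reduce coverage. Neither is a probability of failing to reach saturation. Whichever applies, no stopping rule, test or decision uses saturation. The endpoint is a finalized intervention, content from other sources limits what a missed voice could cost, and Phase 2 requires its own amendment and approval. A range of 5-10 is a fair trade-off for refining an intervention that is already drafted. The conclusion would differ if the plan made a decision conditional on saturation, or if it said that symptomatic caregivers were expected to judge the intervention differently; it does neither.

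### The coding stopping rule in Section 7.3 is printed as kappa >0.080, which contradicts the high reliability it is meant to define

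*Combined protocol and SAP*

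**What the plan says.** The primary endpoint of Phase 1 (Section 7.1.1) is a finalized caregiver intervention, "based on the findings from the qualitative data analysis". Section 7.3 describes that analysis:

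- **Framework.** "Study staff will independently review the qualitative interview transcripts to create a thematic framework for interpretation".
- **Coding.** "Two independent coders" are named. They "will independently code the data to enhance validity and credibility", and they continue "until high reliability is achieved (Kappa >0.080".
- **Disagreements.** "Discrepancies will be resolved by comparison to raw data", with further review by named investigators.
- **Use of the results.** "We will utilize the qualitative data obtained from phase 1 and clinicians' experience to finalize the multicomponent psychological intervention".

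This is the only place where kappa appears. No other section gives a reliability threshold or defines high reliability in another way.

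**The concern.** The sentence sets its standard in words and then gives a number that means nearly the opposite. A kappa of 0.080 is close to chance agreement. Because coding continues until the standard is met, the number acts as a stopping rule. It is also the only numerical reliability criterion for the analysis on which the primary endpoint rests.

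As printed, the rule would accept agreement only slightly better than chance, and anyone auditing adherence would have to count that as compliant. The stake extends a little beyond Phase 1: under Section 5.1 the finalized manual is carried into Phase 2, which the Overview describes as a pilot randomized trial in 100 caregivers.

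**Working it through.** **Inputs.** The printed threshold, 0.080, is from Section 7.3. It is a stated criterion with no calculation behind it, so there is no figure to reproduce. The protocol gives no code frequencies, no number of coded segments and no alternative threshold. Those used below are illustrative assumptions, shown over a range.

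**Definition.** With observed agreement po and chance agreement pe, kappa = (po − pe)/(1 − pe). Hence:

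- required agreement: po = pe + kappa × (1 − pe)
- disagreement: 1 − po = (1 − kappa) × (1 − pe)

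**Meaning of 0.080.** Kappa is the share of the possible agreement beyond chance that is actually achieved. Here that share is 8%.

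**Required raw agreement.** If both coders apply a yes/no code to half the segments, pe = 0.5² + 0.5² = 0.50. If they apply it to 80%, pe = 0.8² + 0.2² = 0.68.

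| Kappa | po, 50/50 code | Disagreements per 100 | po, 80/20 code | Disagreements per 100 |
|---|---|---|---|---|
| 0.08 (printed) | 0.50 + 0.08 × 0.50 = 54% | 46 | 0.68 + 0.08 × 0.32 = 70.6% | 29.4 |
| 0.70 (assumed) | 85% | 15 | 90.4% | 9.6 |
| 0.80 (assumed) | 90% | 10 | 93.6% | 6.4 |
| 0.90 (assumed) | 95% | 5 | 96.8% | 3.2 |

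For the 50/50 code, the printed cut-off asks for 4 percentage points more than chance.

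**Ratio of disagreements.** At the same pe the factor (1 − pe) cancels, so the ratio is 0.92/(1 − intended kappa):

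- intended 0.70: 0.92/0.30 = 3.1
- intended 0.80: 0.92/0.20 = 4.6
- intended 0.90: 0.92/0.10 = 9.2

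**Could random coding pass?** Two coders assigning a 50/50 code purely at random were simulated, with 100,000 runs for each number of segments.

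| Segments | Runs with kappa >0.080 | Runs with kappa >0.80 |
|---|---|---|
| 50 | 29.6% | 0.0% |
| 100 | 21.5% | 0.0% |
| 200 | 13.2% | 0.0% |
| 500 | 3.7% | 0.0% |

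A normal approximation with standard error 1/√n agrees. At n = 50, z = 0.08 × √50 = 0.57, which gives about 29%. At n = 100, z = 0.80, which gives about 21%.

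**The case against.** The strongest reply is that this is a typographical slip with little operational effect. The words state the aim, the figure only glosses them in parentheses, and the trailing zero itself suggests a slipped digit. Two experienced coders would be unlikely to stop near chance agreement. That is a fair reason to keep the point minor. It does not make the figure right, and a reader still has to guess the intended value.

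Three further objections limit how far the numbers go.

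- **The threshold is a floor.** Comparing coders exactly at 0.08 with coders exactly at 0.80 does not predict how these coders will perform. The disagreement counts are also taken before reconciliation, which Section 7.3 applies at any kappa. They therefore measure the laxity of the rule, not error in the final coded data.
- **The rule is not empty.** In the simulation, purely random coding fails the printed cut-off in about 70% of single assessments at 50 segments and 96% at 500. The cut-off is far too low to mean high reliability, but it does exclude something.
- **The figure could have been misread from the PDF.** This cannot be fully excluded, but the sentence is intact running text with no sign of redaction, and the sponsor can settle it from the source file.

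One might add that 15 of the 22 interview-guide items (1–3, 5–15 and 21) have fixed response options and so depend less on coding. That gives only partial comfort. Each of those items also invites free-text comments, and Section 7.3 does not say that the fixed responses are analysed separately.

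**Conclusion.** The inconsistency stands as a minor error in the analysis plan. That 0.080 cannot denote high reliability follows from the definition of kappa alone and needs no outside benchmark.

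The size depends on assumptions. The comparator of 0.80 rests on the inference of a misplaced decimal, and the code frequencies are illustrative. Any intended value from 0.70 to 0.90 leads to the same conclusion. The practical effect is limited by the stated aim, the independent transcript review, the two independent coders, the reconciliation against raw data and the use of clinicians' experience. None of these supplies another numerical criterion. No sample size or error rate is affected.

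**What to change.** The sponsor should check the source, confirm the intended threshold and correct the figure in Section 7.3. The presumed correction is kappa >0.80, but this is an inference for the sponsor to confirm.

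The cost is one figure in the plan. Some of the 5–10 transcripts would need recoding only if coders had already stopped at a kappa below the confirmed value. The protocol is version 1 and reports no coding done.

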## 9 Appendices

### Appendix A: Baseline Questionnaire

#### Caregiver Demographics

Please check the appropriate box or boxes.

1. Date of birth (mm/dd/yyyy) \_\_\_\_\_
  
2. Gender
  - Man
  - Woman
  - Other
  
3. Relationship to patient
  - Married or living as if married
  - Non-cohabiting relationship
  - Divorced/Separate
  - Child (daughter or son)
  - Parent (mother or father)
  - Sibling (brother or sister)
  - Friend
  - Other family
  
4. Ethnicity
  - Hispanic or Latino
  - Not Hispanic or Latino
  
5. Race (please check all that apply)
  - American Indian or Alaskan native
  - Asian
  - African American or Black
  - Native Hawaiian or other Pacific Islander
  - White
  - Other (please specify) \_\_\_\_\_
  
6. Religion
  - Catholic Christian
  - Other Christian (such as Protestant, Orthodox, etc.)
  - Jewish
  - Muslim
  - Atheist
  - None
  - Other (please specify) \_\_\_\_\_

Psychological Intervention to Promote Coping for Caregivers of Patients Undergoing Hematopoietic Stem Cell Transplantation (HCT)  
Protocol version 1/ 10-3-2016

7. Please indicate your highest or current education level

- 11th grade or less
- High school graduate or GED
- 2 years of college/AA degree/Technical school training
- College graduate (BA or BS)
- Masters degree
- Doctorate/Medical degree/Law degree

8. Current employment status

(please check all that apply):

- Employed (full-time or part-time)
- Caring for home or family (not currently employed and not looking for paid work)
- Unemployed and looking for work
- Unable to work due to illness or disability
- Retired
- Student
- Other (please specify) \_\_\_\_\_

9. Please indicate how long you have known the patient: \_\_\_\_\_ years

10. Do you live in the same residence as the patient?

- Yes
- No

Your name: \_\_\_\_\_

Please enter your email address  
(will only be used if necessary):

\_\_\_\_\_

What is the best phone number to use if we needed to reach you?

\_\_\_\_\_

## INTRODUCTION

You recently took part in a study that was designed to help caregivers of patients undergoing hematopoietic stem cell transplantation (HCT) cope most effectively with their loved ones' illness. We are now interested to know about your satisfaction with different aspects of this research study so that we continue to shape how to provide it to patients. There is no right or wrong answer. Your answers will be kept confidential and will not affect your participation in future research studies or your access to medical care.

First, I am going to ask you some questions about the timing of the sessions you had and how they were delivered.

1. This study was scheduled to start 1-2 weeks prior to HCT. How do you feel about the timing of the program?

- A. Right time
- B. Too soon before transplant
- C. Too close to time of transplant

Additional Comments:

2. This study was scheduled to continue through day +70 after HCT. How do you feel about the timing of the program?

- A. Right time
- B. Too short after HCT
- C. Too long after HCT

Additional Comments:

3. The research study was designed so that sessions were scheduled along with your other medical appointments whenever possible. How do you feel about the convenience of attending the sessions?

- A. Convenient
- B. Not convenient
- C. Not sure

Additional Comments:

Psychological Intervention to Promote Coping for Caregivers of Patients Undergoing Hematopoietic Stem Cell Transplantation (HCT)  
Protocol version 1/ 10-3-2016

4. What prevented you from attending the intervention sessions? What would help you attend more of these sessions?

5. The research study was designed so that sessions can be scheduled over the phone when in-person visits were not possible. How do you feel about the phone sessions?

- A. Great
- B. In-person was better
- C. Not sure

Additional Comments:
----------------------

Additional Probe: Would you have preferred all sessions to be delivered over the telephone for convenience?

6. How do you feel about the total number of visits included in this research study (eight visits total)?

- A. Right amount
- B. Too few
- C. Too many

Additional Comments:
----------------------

7. How do you feel about the amount of time each visit lasted?

- A. Right amount
- B. Too short
- C. Too long

Additional Comments:
----------------------

Now I am going to ask you some questions about the material covered in your visits.

8. During these sessions, you may have learned about strategies to help you cope most effectively with your loved ones' illness. How helpful did you find these strategies?

- A. Helpful
- B. Not helpful
- C. Not sure

Additional Comments:
----------------------

Additional Probe: The interviewer can remind the caregiver about specific strategies such as acceptance, mindfulness, problem-solving, self-care, communication techniques, etc. Also ask which of these strategies was the most helpful

Psychological Intervention to Promote Coping for Caregivers of Patients Undergoing Hematopoietic Stem Cell Transplantation (HCT)  
Protocol version 1/ 10-3-2016

9. Since going to the study visits, how often have you used any of these strategies on your own?

- A. Daily
- B. Few times/ week
- C. Once or twice
- D. Never

Additional Comments:

10. During these sessions, you may have learned about skills or strategies that would help you gain more confidence in your ability to care for your loved one. How helpful was it to learn about these skills or strategies?

- A. Helpful
- B. Not helpful
- C. Not sure

Additional Comments:

Additional probe: Which of these strategies was the most helpful?

11. Since going to the study visits, how often have you used any of the skills or strategies on your own?

- A. Daily
- B. Few times/ week
- C. Once or twice
- D. Never

Additional Comments:

12. During these sessions, you may have learned about skills or strategies that would help take better care of yourself during your loved ones' illness. How helpful was it to learn about these skills or strategies?

- A. Helpful
- B. Not helpful
- C. Not sure

Additional Comments:

Additional probe: Which of these strategies was the most helpful?

Psychological Intervention to Promote Coping for Caregivers of Patients Undergoing Hematopoietic Stem Cell Transplantation (HCT)  
Protocol version 1/ 10-3-2016

13. Since going to the study visits, how often have you used any of the skills or strategies on your own?

- A. Daily
- B. Few times/ week
- C. Once or twice
- D. Never

Additional Comments:

14. During these sessions, you may have learned about skills or strategies that would help communicate more effectively with your loved one. How helpful was it to learn about these skills or strategies?

- A. Helpful
- B. Not helpful
- C. Not sure

Additional Comments:

Additional probe: Which of these strategies was the most helpful?

15. Since going to the study visits, how often have you used any of the skills or strategies on your own?

- A. Daily
- B. Few times/ week
- C. Once or twice
- D. Never

Additional Comments:

16. Is there anything else that you found helpful about this program?

17. Is there anything else that you found *not* helpful about this program?

18. What other kinds of programs focusing on improving your well-being (if any) would have been helpful *prior* to your loved ones' stem cell transplantation?

Psychological Intervention to Promote Coping for Caregivers of Patients Undergoing Hematopoietic Stem Cell Transplantation (HCT)  
Protocol version 1/ 10-3-2016

19. What other kinds of programs focusing on improving your well-being (if any) would have been helpful *immediately after* your loved ones' stem cell transplantation?

20. What other kinds of programs focusing on improving your well-being (if any) would be helpful to you now?

21. People learn information in different ways. What would you prefer in terms of how the intervention is administered?

- A. One-on-one visit with a clinician
- B. Reading information from a pamphlet
- C. Watching an informational video
- D. Telephone contact with a clinician
- F. Getting information from a mobile app
- G. Video (skype-like) sessions
- H. Group-based sessions with other caregivers

Additional Comments:

22. Is there anything else that you would like to add that we have not discussed?

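### The exit interview asks no open question on what helped or did not help until after eight fixed-choice content items and an optional probe naming strategies, so unprompted views may be shaped or under-reported

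*Combined protocol and SAP*

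**What the plan says.** Items 1 to 7 of the guide cover timing, convenience, attendance, phone delivery, and the number and length of visits. The content block then opens with "Now I am going to ask you some questions about the material covered in your visits".

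- **Items 8 to 15** all have fixed answers. Items 8, 10, 12 and 14 ask how helpful it was to learn about coping, confidence in caregiving, self-care and communication with the patient. Items 9, 11, 13 and 15 ask how often the skills were used.
- **The item 8 probe** reads "The interviewer can remind the caregiver about specific strategies such as acceptance, mindfulness, problem-solving, self-care, communication techniques, etc". It also has the interviewer ask which strategy helped most.
- **The probe at items 10, 12 and 14** is "Additional probe: Which of these strategies was the most helpful".
- **Item 16** is "Is there anything else that you found helpful about this program". Item 17 asks the same about what was not helpful, with the same residual phrasing.
- **The only earlier stand-alone open item** is item 4, on attendance: "What prevented you from attending the intervention sessions? What would help you attend more of these sessions".
- **Item 22** closes the guide: "Is there anything else that you would like to add that we have not discussed".

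On analysis, section 7.3 states: "Study staff will independently review the qualitative interview transcripts to create a thematic framework for interpretation". It also lists domains fixed in advance, such as preferences, length and timing, and challenges. It plans to use feedback to confirm or revise content and to pick up concerns that the intervention did not cover. Under section 7.1.1 the primary endpoint is the finalized intervention, resting on the qualitative findings.

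**The concern.** Once an interviewer has named a topic, a caregiver's remark about it no longer shows that the topic would have come up unaided. The usual safeguard is to ask the broad question first and the specific ones afterwards. This guide reverses that order for content. By the time caregivers are asked openly what helped, the item stems have named four skill areas and the interviewer may have listed individual strategies. The wording then asks only for what is left over.

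The consequence would be a framework that leans towards the programme's own categories, in a phase meant to find out whether those categories fit. The exit interview is also the only instrument that collects caregivers' views of the intervention: the baseline questionnaire is demographic, and section 5.2 (Selection of study instruments) requires nothing further. No second caregiver source could reveal the effect.

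**Working it through.** Section 7.2 justifies the sample of 5-10 by experience and expected thematic saturation. There is no power or precision figure to reproduce. The check is a count of the guide by format and order, followed by a comparison with the planned uses.

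**Format and order**

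- Fixed-choice: items 1-3, 5-15 and 21, so 3 + 11 + 1 = 15.
- Stand-alone open: items 4, 16-20 and 22, so 1 + 5 + 1 = 7. Total 15 + 7 = 22.
- Fixed-choice items before item 16: 3 + 11 = 14, of which 8 (items 8-15) concern content.
- Stand-alone open items before item 16: 1 (item 4), and it is not about content.

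So no open question on what helped or did not help precedes the first content prompt.

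**Direction of the embedded probes**

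- Probes asking which strategy was most helpful: 4 (items 8, 10, 12, 14).
- Probes asking which was least helpful, or what was missing: 0.

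A caregiver can choose the not-helpful option and comment on it, but item 17 is the first open question devoted to negative views of content.

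**Planned uses set against the order**

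- Confirming the relevance of named content, and revising session number, length and modality: directed questions serve this well, and the order does little harm.
- Building a framework from the transcripts: partly needs unprompted material, so the order matters.
- Finding concerns the intervention left out: items 18-20 and 22 serve this, but they also come after the prompts.

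**Illustration of what under-reporting could do**

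The documents give no rate at which caregivers raise a theme unaided, so every rate below is an assumption. If each of n caregivers independently raises a theme with probability p, the chance of hearing it at least once is 1 − (1 − p)^n. For p = 0.20, this is 1 − 0.8^5 = 0.67 and 1 − 0.8^10 = 0.89. If question order halved the rate to 0.10, it is 1 − 0.9^5 = 0.41 and 1 − 0.9^10 = 0.65.

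| Assumed p | n = 5, no loss | n = 5, p halved | n = 10, no loss | n = 10, p halved |
|---|---|---|---|---|
| 0.10 | 0.41 | 0.23 | 0.65 | 0.40 |
| 0.20 | 0.67 | 0.41 | 0.89 | 0.65 |
| 0.30 | 0.83 | 0.56 | 0.97 | 0.80 |
| 0.50 | 0.97 | 0.76 | 1.00 | 0.94 |

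The no-loss columns are as compatible with the documents as the halved ones. The table shows only that, with so few interviews, less common themes would be the most sensitive to any suppression.

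**The case against.** The case for leaving the guide alone has real substance.

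- **Fixed-choice does not mean closed to talk.** All 15 such items have a comments field. Section 5.2 (Selection of study instruments) tells facilitators to probe, and section 5.4 has every interview recorded and transcribed. This stands, although comments follow a topic the guide has just named.
- **The naming probe is optional, and the stems are not exhaustive.** Four of the eight items ask only about frequency of use. Items 8-15 do not name managing expectations of transplant (session 1) or communication with the health care team (sessions 4 and 5). This stands. The stems of items 8, 10, 12 and 14 are nevertheless scripted for every interview.
- **Caregivers were taught these strategies**, so naming them is a reminder and plants no new idea. This stands in part, since a reminder can still change what a person mentions first.
- **Other routes exist.** Items 18-20 ask about other programmes, and item 22 is a catch-all. This stands for new material, less so for criticism of existing content.

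A reader might go further and infer that unprompted themes are certain to be primed or lost. The routes above make this a risk only. A reader might also treat unprompted themes as the whole basis of the primary endpoint. Much of the planned refinement uses directed feedback, some domains are preset, and clinicians' experience contributes too. Nor are prompted and unprompted remarks inseparable, because a transcript shows what the interviewer had already said.

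Finally, about 30 minutes for 22 items plus 5 probes averages 1800/27 = 67 to 1800/22 = 82 seconds each, which might suggest that the last open items get cut. That average assumes equal time per item, and the plan sets no cut-off, so it is not evidence of truncation.

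**Conclusion.** The point holds as a limited and correctable weakness of order and wording. No open question on helpfulness comes before the content prompts, the embedded probes look only for what helped most, and the first dedicated open question on unhelpful content is item 17, worded as a remainder. Views that the framework and the search for missed concerns partly depend on may therefore be primed or under-reported.

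The size is unknown and could be small. The item counts describe the instrument and do not measure bias. The conclusion assumes that interviewers broadly follow the printed order and do not, on their own initiative, open the content block with a free question. A semi-structured format would let them do so, but the guide does not ask for it. The change is worth making before the first exit interview, because an unprompted answer cannot be recovered from a caregiver who has already been through the prompts.

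**What to change.** 1. In Appendix B, insert an open pair at the start of the content block, before item 8: *In your own words, what, if anything, about this program did you find helpful? What, if anything, did you find not helpful?*
2. Keep items 8 to 15 unchanged, so the directed feedback is preserved.
3. Keep items 16, 17 and 22 as follow-ups. Their residual wording then fits, because an open question has gone before.
4. In section 7.3, state that answers to the new pair are coded as unprompted, and that later remarks on topics already named by the guide or the interviewer are coded as prompted. Position before item 8 should not by itself define unprompted, since answers to items 1-3 and 5-7 respond to fixed-choice questions. A new topic raised at items 18-20 or 22 should not be labelled prompted merely because it came late.

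The cost is a minute or two of interview time and one extra code. First answers may be brief before any reminder, but the directed items still follow. Sample size, visits and staffing do not change.
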